5.1. Summary of Study Design

Study I4V-MC-JAHV (JAHV) is a multicenter, randomized, double-blind, placebo-controlled, medication-withdrawal study with a safety/pharmacokinetic (PK) assessment period, an open-label lead-in (OLLI) period, and a double-blind withdrawal (DBW) period in patients with JIA who have had an inadequate response or intolerance to treatment with at least 1 other conventional or bDMARD. This includes patients with polyarticular JIA (rheumatoid factor positive or rheumatoid factor negative), extended oligoarticular course JIA, enthesitis-related JIA (ERA), and juvenile psoriatic arthritis (JPsA) as defined by the International League of Associations for Rheumatology (ILAR) criteria. The safety and tolerability data from this study are intended to establish an understanding of the benefit/risk relationship for baricitinib in patients with nonsystemic JIA.

Abbreviations: OLE = open-label extension; PediACR30 = Pediatric American College of Rheumatology 30 criteria; PK = pharmacokinetic(s); QD = once daily.

- Staggered approach to enrollment by age group (12 to <18 years, 9 to <12 years, 6 to <9 years, 2 to <6 years) will be implemented with older groups completing the safety/PK assessment period before younger groups are enrolled.
- Once the PK and safety profiles for an age group are confirmed, subsequent patients in that age group may enroll directly into the OLLI period. If the comparability assessment in the safety/PK period for an age group is inconsistent with baricitinib 4-mg exposures in adults with RA such that baricitinib dosage for the age group needs to be adjusted, the patients on the inconsistent dosage will discontinue the study and may enter the separate OLE study (JAHX).
- Patients who experience a disease flare during the DBW period will discontinue the study and may proceed directly to the separate OLE study (JAHX).

Figure JAHV.1. Study design for Clinical Protocol I4V-MC-JAHV.

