5.2. Determination of Sample Size

A total of 128 patients will be randomized in a 1:1 ratio to baricitinib or placebo (64 per treatment arm) in the DBW period. This sample size will provide approximately 80% power to detect the difference in time to disease flare between the 2 treatment groups using a 2-sided test with a significance level of 0.05, assuming that the expected percentages of patients experiencing disease flare in the DBW period are 35% for baricitinib and 60% for placebo and that the dropout rate is no greater than 10% in this period.

It is estimated that 197 patients are required to enter the OLLI period to allow 128 patients to be randomized into the DBW period (assuming that 65% of the patients meet the Pediatric American College of Rheumatology (PedACR) 30 criteria at the end of the OLLI period). The nonresponder and dropout rate will be monitored during the OLLI period to adjust the overall sample size to ensure that a minimum of 128 patients will be randomized in the DBW. If the

PedACR30 response rate during the OLLI period is higher than the assumed rate of 65%, fewer than 197 patients may be required.

The above sample size and power estimates are based on nQuery[®]+nTerim 4.0.

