6.1.3. Definition of OLLI and DBW Analysis Periods

The OLLI period starts at:

- The completion of Safety/PK assessment period for Safety/PK population patients
- The time of first age-based dose of baricitinib for OLLI population patients

The OLLI period ends for the following study events:

- Week 12 (Visit 9) for patients who do not meet the randomization criteria, or
- Visit of early discontinuation of study treatment in the OLLI period.

The DBW period starts at the time of randomization and ends at the following study events:

- Patient experience disease flare (defined in [Table JAHV.6.4](#))
- Week 44 (Visit 17) for patients who do not flare, or
- Visit of early discontinuation of study treatment in the randomized double-blind withdrawal period.

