The primary safety analysis will be conducted during the DBW period for the DBW safety population. Fisher's exact test will be used for the adverse events (AEs), discontinuation, and other categorical safety data for between-treatment group comparisons. Continuous vital signs, body weight, and other continuous safety variables, including laboratory variables will be analyzed by an ANCOVA with treatment group and baseline value in the model. The significance of within-treatment group changes from baseline will be evaluated by testing whether or not the treatment group LSM changes from baseline are different from zero; the standard error and within-group p-value for the LSM change will also be displayed. In addition, the LSM difference between baricitinib and placebo groups, the corresponding p-value, and 95% CI will be provided. Treatment-emergent high/low for categorical laboratory safety analyses will also be produced.

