Postbaseline for LLT used in defining treatment-emergence and change from baseline analysis	
The event start time (onset time) is on or after first dose of baricitinib in Safety/PK assessment period or OLLI period, before time of randomization in DBW period (include up to 30 days off-drug follow-up time if patient did not enter DBW period).
 
For treatment-emergent abnormal labs, vital signs and shift summaries in labs, all scheduled and unscheduled measurements will be included.
 
For change from baseline labs, vital signs and growth, only scheduled visits will be included. The early termination visits (ETV) are considered scheduled visits.
	
The event start time (onset time) is on or after time of randomization in DBW period, up to 30 days off-drug follow-up time.
 
For treatment-emergent abnormal labs, vital signs and shift summaries in labs, all scheduled and unscheduled measurements will be included.
 
For change from baseline labs, vital signs and growth, only scheduled visits will be included. The early termination visits (ETV) are considered scheduled visits.
	

Abbreviations: Bari = baricitinib; DBW = double-blind withdrawal; OLLI = open-label lead-in; JIA = juvenile idiopathic arthritis; LLT = Lowest Level Term; PK = pharmacokinetics.

Safety topics that will be addressed include the following: AEs, clinical laboratory evaluations, vital signs and physical characteristics, safety in special groups and circumstances, including adverse events of special interest (AESI) (see Section 6.18.5).

Unless otherwise specified, by-visit summaries will include planned on-treatment visits. For tables that summarize events (such as AEs, categorical lab abnormalities, shift to maximum value), post-last dose follow-up data will be included. For deaths and malignancies, all available follow-up data up to the end of the study will be included. Listings will include all safety data.

The following statistical methods will be used for safety analysis during the DBW period with the DBW safety population unless otherwise noted:

- The Fisher exact test will be used for treatment comparisons of proportions, and odds ratios with corresponding 95% confidence intervals will be provided.
- Treatment differences in mean change for continuous measurements will be assessed using an ANCOVA model fitting “baseline” as a covariate. Type 3 sums of squares will be used.

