Though p-values will be provided for many of the safety analyses, they should not be overinterpreted. They correspond to data-driven hypotheses and are only useful as a flagging mechanism.

Statistical significance is designated at 2-sided p-values (rounding up to 3 decimal places) ≤ 0.05 for tests of treatment differences. However, p-values should not be overinterpreted.

Exposure-adjusted incidence rate (EAIR) will be provided for selected topics. The EAIR is evaluating the incidence of a first event per 100 patient-years at risk (PYR). Exposure will be calculated based on the analysis period defined as the treatment period plus up to 30 days off-drug follow-up time. Exposure time for a patient with an event will be counted up to the time of the start of event. Exposure time for a patient without an event will be censored at the end of the analysis period. For each EAIR provided, a Poisson distribution 95% CI may be calculated. Treatment group comparisons, when provided, will be provided based on the incidence rate difference (IRD) together with its 95% CI.

Not all displays described in this SAP will necessarily be included in the CSR. Any display described in this SAP and not provided in the CSR would be available upon request. Not all displays will necessarily be created as a “static” display. Some may be incorporated into interactive display tools instead of or in addition to a static display. Any display created interactively will be included in the CSR if deemed relevant to the discussion.

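### Flare ends DBW follow-up sooner on placebo, yet the standard adverse-event comparison uses crude proportions; report the rate and rate difference that the SAP already defines beside them (minor).

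*SAP*

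**What the plan says.** - **End of follow-up.** SAP 6.1.3: "The DBW period starts at the time of randomization and ends at the following study events". Disease flare is the first event listed. The design-figure footnote in SAP 5.1 states: "Patients who experience a disease flare during the DBW period will discontinue the study".
- **Planned flare.** SAP 5.2 assumes "35% for baricitinib and 60% for placebo", with 64 patients per arm and at most 10% dropout.
- **Safety comparison.** SAP 6.1.4 makes the DBW period the primary safety analysis, where Fisher's "exact test will be used for the adverse events (AEs), discontinuation, and other categorical safety data for between-treatment group comparisons". SAP 6.18 repeats this: "The Fisher exact test will be used for treatment comparisons of proportions, and odds ratios with corresponding 95% confidence intervals will be provided". The adverse-event (AE) summaries in Table JAHV.6.11 are counts and percentages of patients.
- **Rates.** SAP 6.18 also says "Exposure-adjusted incidence rate (EAIR) will be provided for selected topics". It defines the rate as first events per 100 patient-years at risk, counting up to 30 off-drug days. On between-arm contrasts it says "Treatment group comparisons, when provided, will be provided based on the incidence rate difference (IRD", with a 95% CI. The topics are not named in this SAP.
- **What already helps.** SAP 6.18.1 reports total patient-years of exposure. SAP 6.18 says of safety p-values: "They correspond to data-driven hypotheses and are only useful as a flagging mechanism". SAP 6.21.1 gives the DMC incidence rates where they apply.
- **Other sources.** SAP 6.18 and 6.18.2 place some detail in compound-level safety standards. Protocol 10.3.4.1 lets the analysis of AEs of special interest sit in a program safety analysis plan, which SAP section 8 lists as a report on file. None of these was available for this review.

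**The concern.** If baricitinib works as planned, placebo patients flare earlier and leave earlier, so they have less time in which an AE can be recorded. Two arms with the same AE hazard would then show different percentages, and Fisher's test and the odds ratio would read the difference as a drug effect. In a paediatric trial whose safety data are meant to inform benefit and risk, a reader of the primary safety tables should be able to separate longer observation from a higher event rate. The SAP already holds the tool for this but does not commit to it for the main DBW tables.

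**Working it through.** **1. The plan's own figure.** Under constant hazards HR = ln(0.65)/ln(0.40) = 0.470.
- Schoenfeld, 10% removed: D = 128 × 0.9 × 0.475 = 54.7 events. Power = Φ(√54.7 × 0.755/2 − 1.96) = 79.7%.
- Freedman, no dropout: D = 128 × 0.475 = 60.8 events. Power = Φ(√60.8 × (1 − 0.470)/(1 + 0.470) − 1.96) = 80.2%.

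The stated 80% reproduces, so the flare assumptions are used below as they stand.

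**2. Time at risk.** Inputs: flare 35% and 60% over 32 weeks, 10% dropout, 64 per arm (SAP 5.2); visits every 4 weeks (Protocol section 2). Flare hazards per week: −ln(0.65)/32 = 0.01346 and −ln(0.40)/32 = 0.02863.
- Continuous detection, no dropout: mean = p/λ = 0.35/0.01346 = 26.0 and 0.60/0.02863 = 20.9 weeks; ratio 1.24.
- Base case (flare recorded at the next 4-weekly visit, exponential dropout): 25.4 and 21.2 weeks; ratio 1.20. With 64 per arm this is about 31.2 and 26.0 patient-years.
- Base case plus 30 days (4.29 weeks) for everyone: (25.44 + 4.29)/(21.21 + 4.29) = 1.17. This is an upper limit for the tail, because patients who enter the extension need no follow-up visit (Protocol 5.1.5).

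The documents do not give flare timing. With continuous detection and no dropout, Weibull shapes from 0.5 to 2 give ratios from 1.36 to 1.14.

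**3. Effect on the crude comparison.** Assumption: the AE hazard is constant, equal in both arms and independent of flare. It is scaled to a chosen 32-week risk. Incidence is the mean of 1 − exp(−hT) over the base-case follow-up times T. The OR interval is Woolf's at the expected counts. Fisher rejection is an exact enumeration at 64 per arm, two-sided p ≤ 0.05.

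| 32-week AE risk | Baricitinib vs placebo | Crude OR (95% CI) | Fisher rejection |
|---|---|---|---|
| 5% | 4.0% vs 3.3% | 1.21 (0.19–7.69) | 0.8% |
| 10% | 8.0% vs 6.7% | 1.21 (0.32–4.60) | 2.3% |
| 20% | 16.1% vs 13.5% | 1.23 (0.46–3.26) | 4.1% |
| 30% | 24.2% vs 20.5% | 1.24 (0.54–2.86) | 5.2% |
| 50% | 41.0% vs 35.0% | 1.29 (0.63–2.63) | 8.0% |
| 70% | 58.6% vs 51.0% | 1.36 (0.68–2.73) | 10.1% |
| 90% | 78.3% vs 70.5% | 1.52 (0.68–3.38) | 12.7% |

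In patients, the excess is 64 × (0.161 − 0.135), about 1.6 or 1.7, in the 20% row and 64 × (0.783 − 0.705) = 5.0 in the last row. In the 50% row, 7.8 of the 8.0 points are rejections against baricitinib. With the full 30-day tail, rejection is at most 9.0%. It reaches 19.3% only with continuous detection, no dropout and a 90% AE risk together.

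**4. How the rate behaves.** Under constant equal hazards the exposure-adjusted rate ratio is 1.00. It is not neutral otherwise:
- AE hazard three times higher in weeks 0 to 4: crude ratio 1.07–1.14, rate ratio 0.95–0.96. Five times higher: 1.05–1.11 and 0.93–0.94.
- If 5%, 10% or 20% of flares bring a first AE, on a 20% background risk: crude ratio 1.09, 1.02, 0.93; rate ratio 0.92, 0.86, 0.78. On a 50% background risk: 1.13, 1.11, 1.05 and 0.97, 0.95, 0.90.

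**5. What a reader can already approximate.** Dividing patients with an event (Table JAHV.6.11) by total patient-years (SAP 6.18.1) gives a between-arm ratio of 0.97 to 1.00 for risks up to 50%, 0.96 at 70% and 0.93 at 90%.

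**The case against.** The strongest reply is that little is lost. Step 5 shows that simple division recovers most of the adjustment. This stands, with two limits: the exposure in SAP 6.18.1 stops at last dose while AE tables include up to 30 off-drug days, and it is not time to first event.

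Second, the EAIR topics may be listed in the compound-level standards or the program safety analysis plan, and the protocol allows that for events of special interest. This also stands. A reader might infer that the sponsor has no exposure-adjusted safety analysis; the documents do not support that, since SAP 6.18 commits to one for some topics.

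Third, the effect is small beside the precision at 64 per arm, the SAP warns against overreading safety p-values, and no decision rule in the SAP uses them. Agreed. This makes the point minor but does not remove the displacement from the odds ratio.

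Fourth, crude proportions legitimately describe what patients experience when treatment continues or is withdrawn until flare, and the rate has its own bias. Agreed, which is why the rate belongs beside them and not in their place.

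**Conclusion.** The point holds as a minor improvement. By design, time at risk is about 1.2 times longer on baricitinib if the planning assumptions hold, and the prescribed crude contrast does not account for it. With equal constant AE hazards the crude OR is about 1.2 to 1.5 against baricitinib. False flags are at or near 5%, or below, for incidences up to about 25%, and about 8% to 13% only for frequent aggregates.

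A reader might infer that the unequal follow-up conceals harm. Under these assumptions it runs the other way: it overstates harm on baricitinib. That direction depends on AEs being independent of flare; it reversed in one of the flare-linked cases tried (crude ratio 0.93, where 20% of flares bring an AE on a 20% background). A reader might also infer that the tables leave the unequal follow-up invisible. They do not, because patient-years by arm and event counts are both planned.

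The sizes rest on assumed AE rates and flare timing, neither of which the documents give.

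**What to change.** In SAP 6.18, for the main DBW AE summaries (at least any treatment-emergent event, and also serious events, events of special interest and discontinuation due to an AE), report as standard the rate per 100 patient-years at risk by arm and the rate difference with its 95% CI, exact where events are sparse. Keep crude n (%), Fisher's test and the odds ratio. Add a note that the crude contrasts reflect unequal follow-up and that both measures should be read together. If the compound-level standards or the program safety analysis plan already specify this for these summaries, citing them in 6.18 is enough. Laboratory shift tables can stay as they are.

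Cost: SAP wording and some table programming with a method already defined. Fisher's test keeps its role under Protocol 10.3.4. If the addition counts as a change of method that leaves the protocol's principal features intact, Protocol 10.3.1 asks only that it be described and justified in the study report. Downside: the rate assumes a roughly constant hazard, slightly favours baricitinib when AEs come early, and does not correct for flare-linked AEs, so it must not replace the crude results.

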6.2. Adjustments for Covariates

The randomization to treatment groups at Week 12 (Visit 9) is stratified by:

- history of prior bDMARD use (Yes versus No)
- the JIA categories
 - polyarticular and extended oligoarticular [combined] or
 - enthesitis-related JIA and JPsA [combined]
- predose exposure ESR categories (elevated [>20 mm/hour] and not elevated) in the polyarticular JIA patients

Unless otherwise specified, the statistical analysis models will adjust for JIA patient category (polyarticular and extended oligoarticular versus ERA and JPsA), history of prior bDMARD use (Yes or No), and predose exposure ESR categories (above 20 mm/L or below 20 mm/L). If any of these are redundant for a particular model, they will be dropped. The covariates used in the ANCOVA model for continuous data generally will include the parameter value at baseline. When an MMRM analysis is performed, baseline value and baseline-by-visit interactions will be included as covariates.

6.3. Handling of Dropouts or Missing Data

Intercurrent events (ICH E9R1) are events which occur after the treatment initiation and make it impossible to measure a variable or influence how it should be interpreted. Examples of such events include treatment discontinuation due to death or AEs, and loss to follow-up. In this study, intercurrent events will be handled by the while-on-treatment strategy and the composite strategy approaches as primary strategies. The hypothetical strategy will also be used in supplementary analysis.

The *censoring rule*: The efficacy and health outcome data collected after permanent study drug discontinuation will be excluded from the analyses. This censoring rule will be applied to all continuous and categorical efficacy and health outcome endpoints.

For binary response variables that are derived from component scores, the following steps will be implemented unless otherwise specified: If all component scores are missing at a visit, the response status will be set to nonresponse; if at least 1 component score is nonmissing at a visit, the LOCF approach will be applied to impute the missing components within a treatment period. If the binary response status still cannot be determined after LOCF, the binary response status will be set to nonresponse. The detail of the missing data definition and imputation rule is documented in [Table JAHV.6.4](#) and [Table JAHV.6.5](#).

6.3.1. Last Observation Carried Forward (LOCF)

According to ICH E9 R1, the while-on-treatment strategy could be applied based on the last postbaseline value at or before the visit of interest while the patient was still on study drug. The primary endpoint for efficacy evaluation, time to disease flare, is an endpoint that reflects loss of

treatment effect. Therefore, for patients who completed DBW via flare, the LOCF values appropriately estimate their disease status at this time and beyond.

All continuous endpoints will be imputed using the LOCF methodology after applying the censoring rule to those who discontinued study drug. For patients who permanently discontinue study treatment or discontinue from the study for any reason at any time, the last nonmissing postbaseline observation on or prior to discontinuation will be carried forward to subsequent time points for evaluation. LOCF will not be applied across OLLI and DBW analysis periods.

6.3.2. Non-Responder Imputation (NRI)

A non-responder imputation (NRI) imputation method can be justified based on the composite strategy (ICH E9R1) for handling intercurrent events. In this strategy a patient is defined as a responder only if (i) they meet the clinical requirements for response at the predefined time and (ii) they remain on the assigned study treatment. Failing either criteria by definition makes them a non-responder.

Binary efficacy and health outcome variables will be imputed using NRI after applying the censoring rule to those who discontinued study drug. Patients will be considered a non-responder for the NRI analysis if they do not meet the clinical response criteria or are entirely missing the visit at the analysis time point. Randomized patients without at least 1 postbaseline observation will also be defined as non-responders for the NRI analysis.

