Patient visit and data collection can be done remotely for OLLI visits following the protocol visit windows. The PI/Sub-I is to document all teleconferences/remote visits in the patient's records. Site facing assessments will be completed on paper (preferably eCOA if the site is able) and patient facing assessments will be conducted in interview format with the PI/SubI or other qualified personnel documenting the patient's responses on paper. Sponsor will provide guidance for performing these assessments (CHQ-PF50, EQ-5D-Y). Patients *cannot* proceed in JAHV past Visit 9 due to the requirement of PedACR30 responder/nonresponder criteria being defined at this visit to determine eligibility for randomization into DBW phase. Because most PedACR components cannot be collected by remote assessment, patients will be terminated from JAHV at Visit 9 and offered enrollment into JAHX (long term extension).

3. Investigational product and ancillary supplies (including participant diaries)

In cases when a patient is unable to come to the site to receive trial supplies during a normal on-site visit, the site should work with the sponsor to determine appropriate actions to receive trial supplies. This may include a participant coming to the site to receive trial supplies only from site staff without full completion of a visit, a participant-approved designee coming to the site to receive trial supplies on a participant's behalf, or delivery to a participant's home.

The following requirements must be met:

- sponsor approves the alternative method of delivery, taking local regulatory requirements into consideration
- participant consents to alternate method of delivery
- site confirms the participant's receipt of the trial supplies
- site/sponsor confirms appropriate ethics review board notification
- alternate delivery of IP should be performed in a manner that does not compromise treatment blinding and ensures product integrity. The existing protocol requirements for product accountability remain unchanged.
- when delivering supplies to a participant's home:
 - participant consent must include provision of any personal information
 - site should ensure oversight of the shipping process to ensure accountability and product quality (i.e., storage conditions and intact packaging upon receipt)
- additional instructions should be provided to the participant on how to return any unused or completed trial supplies.

4. Local laboratory option

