In exceptional circumstances, to ensure patient safety and with the sponsor's prior written approval, local laboratory testing may be conducted in lieu of central laboratory testing. The local laboratory must be qualified in accordance with local regulations. Clinically significant laboratory findings must be recorded as an AE in the AE eCRF.

For patients unable to access investigator sites, laboratory testing will be conducted at least every 8 weeks in the OLLI and DBW periods. The first collection should be 8 weeks from the patient's last collected central laboratory samples.

Failure to have labs collected within the described ranges above may result in patient termination from the study.

When collecting local labs, sites should store records from the labs including results, address, certification (College of American Pathologists/Clinical Laboratory Improvement Amendments [CAP/CLIA]) status, and reference ranges. The PI/Sub-I should sign and date review of local labs per normal process and follow-up with the patient as needed. Local labs may be sent to the patient as this is standard process in clinical care.

Note: Any results that are obtained from local laboratories will need to be retained by the investigator for their respective patients.

The laboratory measures listed below are the **minimum** required in order to monitor patient safety and determine temporary or permanent discontinuation of IP. Additionally, investigators should include any symptom-based laboratory testing based on their interactions with the patients. As stated in the protocol, investigators are responsible for monitoring the overall health of their patients.

The investigators should request the following laboratory analyses for these select parameters:

- WBC
- ANC
- Lymphocyte count
- Hemoglobin
- Platelet count
- ALT, AST, total bilirubin, INR
- ESR
- Urine pregnancy

These laboratory results will allow the investigators to follow both the temporary and permanent discontinuation criteria as provided in the protocol (Section 8.1.1 Temporary Interruption of Investigational Product and Section 8.1.2. Permanent Discontinuation from Investigational Product)

5. Documentation

a. Changes to study conduct

Changes to study conduct will be documented as the following:

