- Sites will need to identify and document the details of how all participants, visits, methods, and activities conducted were affected by exceptional circumstances. All dispensing/shipment records of IP and relevant communications, including delegation, should be filed with site trial records.
- The site should document the participant's verbal consent for having remote visits and remote dispensing of IP and/or ancillaries prior to implementation of these activities.
- Source document(s) that are generated at an off-site location (e.g., participant's home) should be part of the investigator's source documentation and should be transferred to the site in a secure and timely manner.

b. Missing data and other protocol deviations

The study site should capture specific explanations for any missing data and other protocol deviations in source documents and eCRFs. While protocol deviations may be unavoidable in an exceptional circumstance, documentation of deviations and missing data will be important for data analysis and reporting.

Details of changes in analyses to specifically accommodate exceptional circumstances will be further described in the study SAP.

6. Informing ethical review boards (ERBs)

The sponsor and study investigators will notify ERBs as soon as possible to communicate implementation of changes in study conduct due to exceptional circumstances. To protect the safety of study participants, urgent changes may be implemented before such communications are made, but all changes will be reported as soon as possible following implementation.

Appendix 9. Protocol Amendment I4V-MC-JAHV(d) Summary - A Randomized, Double-Blind, Placebo- Controlled, Withdrawal, Safety and Efficacy Study of Oral Baricitinib in Patients from 2 Years to Less Than 18 Years Old with Juvenile Idiopathic Arthritis (JIA)

Overview

Protocol I4V-MC-JAHV—A Randomized, Double-Blind, Placebo-Controlled, Withdrawal, Safety and Efficacy Study of Oral Baricitinib in Patients from 2 Years to Less Than 18 Years Old with Juvenile Idiopathic Arthritis (JIA)—has been amended. The new protocol is indicated by amendment (d) and will be used to conduct the study in place of any preceding version of the protocol.

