The OLLI patients (Section 6.1.1) who discontinue early will be included. The patients who have important protocol deviations will be excluded; the detail is described in Section 6.20. The missing data imputation rule will align with Section 6.3 and Table JAHV.6.4 for PedACR(ESR) 30 response imputation. The study will stop for futility if the proportion of patient who achieve PedACR(ESR) 30 response is less than 50%. The futility analysis will be based on the observed response rate, no statistical inference will be conducted.

Unblinding details are given in Section 7.

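### The SAP has no efficacy rule for children whose open-label visits were remote, so an administrative exit at Visit 9 can be scored as nonresponse or on carried-forward values in the OLLI PedACR rates

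*SAP*

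**What the plan says.** Protocol Appendix 8, item 2: "Patient visit and data collection can be done remotely for OLLI visits following the protocol visit windows". The same item gives the limit: "Because most PedACR components cannot be collected by remote assessment, patients will be terminated from JAHV at Visit 9". These children are offered the extension study. Item 5b hands the statistical consequences on: "Details of changes in analyses to specifically accommodate exceptional circumstances will be further described in the study SAP".

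SAP 6.19 (COVID-19 Trial Impact) provides a summary of the type of impact, a listing of COVID-19-related discontinuations, and a listing and summary of COVID-19 adverse events. It does not mention efficacy data from remote visits. The general rules therefore apply:

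- SAP 6.3: "If all component scores are missing at a visit, the response status will be set to nonresponse". If at least one component is present, the missing ones are carried forward within the treatment period. If status is still undetermined, it is nonresponse.
- SAP 6.3.1: only postbaseline values are carried forward.
- SAP 6.3.2: patients who "are entirely missing the visit at the analysis time point" are nonresponders.
- SAP Table JAHV.6.4, PedACR response: more than three missing components means nonresponder. Further detail is left to a separate algorithm document.
- Protocol 10.3.1: anyone who discontinues the study is a nonresponder from that time onward.

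For futility, SAP 6.21 says: "The missing data imputation rule will align with Section 6.3 and Table JAHV.6.4 for PedACR(ESR) 30 response imputation". The study stops if fewer than 50% of the first 100 children respond.

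**The concern.** A child ended at Visit 9 under Appendix 8 leaves because response could not be assessed. The exit says nothing about the drug, yet the rules above treat it like any other missing response. The OLLI PedACR30/50/70/90/100 rates are the first secondary endpoints listed in SAP Table JAHV.4.2. They have no comparator arm in which a scoring artefact would cancel. The PedACR30 rate also drives the futility rule. The protocol foresaw the problem and assigned it to the SAP, which is silent on it.

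**Working it through.** **Which rule catches a remote Visit 9?** There are six components: two joint counts, physician global, parent global, CHAQ function and ESR. Appendix 8 says most cannot be collected remotely but does not name them.

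- *No component recorded, or visit entirely missing:* nonresponse (SAP 6.3, 6.3.2).
- *More than three missing:* nonresponse (Table JAHV.6.4). As an illustration, if the two joint counts and physician global are missing, that is three and does not trigger the rule. A missing ESR would be the fourth. ESR can be missing because "For patients unable to access investigator sites, laboratory testing will be conducted at least every 8 weeks in the OLLI and DBW periods", so a result need not fall at every visit.
- *Three or fewer missing:* the missing components are carried forward from the last OLLI visit that has them. For a child entering OLLI directly, a remote Week 2 visit has no earlier postbaseline value to carry.
- *Protocol 10.3.1 read literally:* a child terminated at Visit 9 has discontinued and is a nonresponder at Week 12 even if some components were recorded. The SAP component rule could score the same child a responder.

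The visible text does not say whether the count of missing components is taken before or after carrying forward.

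**The plan's own figure.** Protocol 10.1 and SAP 5.2 assume a 65% PedACR30 rate and need 128 randomized: 128/0.65 = 196.9, rounded up to 197, as stated.

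**Nonresponder route (upper bound).** Inputs are the 65% rate and an assumed share f of children, all scored nonresponse, whose true rate would also have been 65%. Reported rate = 0.65 × (1 − f). Stop chance = P(X ≤ 49), with X binomial (100, reported rate).

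| f | Reported rate | Chance of futility stop |
|---|---|---|
| 0% | 65.0% | 0.07% |
| 5% | 61.8% | 0.6% |
| 10% | 58.5% | 3.5% |
| 20% | 52.0% | 31% |

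The reported rate reaches 50% at f = 1 − 0.50/0.65 = 23.1%.

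**Carry-forward route.** Let c be the response rate that carried-forward values give among remote children (also an assumption). Reported rate = 0.65 × (1 − f) + c × f. At f = 10%:

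| c | Reported rate |
|---|---|
| 45% | 63.0% |
| 55% | 64.0% |
| 65% | 65.0% |
| 70% | 65.5% |

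Even at c = 45%, the stop chance is 0.3% at f = 10%. At f = 20% the rate is 61.0% and the stop chance 1.0%. The shift is smaller and its sign depends on c.

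**The case against.** The strongest reply is that a remote visit is not a missing visit. Appendix 8 still calls for patient-facing questionnaires by interview and for site-facing assessments on paper or eCOA, and ESR is on its local laboratory list. Many remote children would then go to carry-forward and not to nonresponse. This stands, and it is why the first table is an upper bound.

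A reader might infer that joint counts and physician global are declared uncollectable. The protocol names no component. Loss of the joint counts is a reasonable inference from how an active joint is defined, but loss of physician global is less certain. A reader might also infer that every remote child becomes a nonresponder. The rules above do not support that.

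Other limits also stand. Appendix 8 measures are temporary, case by case and need written sponsor approval, so f may be small. A child remote only at earlier OLLI visits may be assessed on site at Visit 9. OLLI results are summarized without inference (SAP 6.1.4).

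On futility, Appendix 8 records missing data as protocol deviations. SAP 6.20 excludes OLLI deviations before Week 12 that could affect the futility analysis. That is a route to exclusion but not a stated one. The choice is left to review meetings and a separate document, and a deviation arising at Visit 9 itself may not count as before Week 12. The PedACR algorithm document may also hold a rule not visible here.

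**Conclusion.** The gap is real: the protocol promised analysis changes for exceptional circumstances, and the SAP gives none for efficacy. The OLLI PedACR rates can be distorted by administrative exits, downward on the nonresponder route and in either direction, by less, on the carry-forward route. The largest effect is a fall from 65% to 61.8%, 58.5% or 52.0% at f = 5%, 10% or 20%. This rests on a true rate of 65%, on remote children responding like the others, and on all of them being scored nonresponse. The documents give no value for f. The matching futility-stop chances (0.6%, 3.5%, 31%) apply only if these children stay among the 100.

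It would go too far to say that the rates must fall, or that they would track the pandemic and not the drug. The rate depends on both, and carry-forward has no fixed direction. The double-blind comparison is not affected, because only children with PedACR30 response established at Week 12 are randomized. Enrolment may be raised to reach 128.

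**What to change.** - **SAP 6.19:** flag remote OLLI visits, and children ended at Visit 9 solely under Appendix 8 item 2. Appendix 8 already has the visit method and the reasons for missing data entered in the eCRF.
- **SAP 6.3 and Table JAHV.6.4:** reconcile the component rule with Protocol 10.3.1 for these children, and say whether missing components are counted before or after carrying forward.
- **Table JAHV.6.5:** keep the planned OLLI PedACR summary. Add a supplementary one that leaves out only the flagged visits and children, or multiply imputes them, and keeps nonresponse for all other discontinuations. Restricting it to everyone assessed on site would also drop children who left for lack of effect or adverse events, and so bias the rate upward.
- **SAP 6.20 and 6.21:** state that flagged children are excluded from the futility set and each replaced by the next evaluable child.

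The cost is SAP wording, one extra summary with somewhat wider intervals, and a futility set that may fill slightly later. At a 65% rate, the 95% half-width, 1.96 × √(0.65 × 0.35/n), is 6.7 points with all 197 children. It is 7.0 points with 177 (10% left out) and 7.4 with 158 (20% left out).
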